## 2. Objectives and Hypotheses

Related to the online focus groups, message testing, and social media components:

[figure not shown]
- 1) Identify HPV vaccine themes/messages/materials and measure their effectiveness to change parent attitudes and intentions to vaccinate their adolescent children;
- 2) Describe any differences in message/material effectiveness for parents residing in rural areas versus parents residing in urban areas
- 3) Launch a social media campaign with the most effective messages to improve parent attitudes.

[figure not shown]

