  - c. *Technical:* Access to all electronic files will be limited to CITI-trained research team members. Audio recordings of the focus groups will be destroyed after transcription. Electronic data will be stored on secure servers housed at DHMC with appropriate backup and will be shared across the research team using the research team's password-protected SharePoint site hosted by Dartmouth.

2. **Online message testing (Phase 2)** - Once the list of strong candidate themes is finalized, we will test the effects of those theme-relevant messages/materials on changing knowledge, attitudes, beliefs, and behavioral intentions of parents of children 9-14 years old living in New Hampshire and Vermont; (parents of any age child are invited to complete the survey as well, excluding questions related to vaccination history and intention to vaccinate). The message testing phase will involve pre/post-test designs. Prior to the message-testing phase (Phase 2), if needed, we will conduct anonymous online pilot surveys through Qualtrics. Prior to the message testing, this pilot test is to check the validity of each message (e.g., ensuring that the stimulus materials -campaign messages- are presented and perceived by audiences as we intended for positive effects).

To test the persuasion effects of candidate messages, we will measure an array of constructs in the pre-test stage (before exposure to materials/messages). A list of the candidate constructs that are critical in understanding message effectiveness include: prior knowledge, pre-existing attitudes, normative beliefs, response efficacy, and issue involvement. After finishing pre-test assessments, participants will be randomly assigned to one of the conditions and asked to read/review the stimulus material/message while experimentally controlling for high elaboration likelihood. After the message exposure step, participants will be asked to answer post-test survey measures, including: persuasiveness of the viewed message/material, attitude toward behavior promoted, response efficacy, behavioral intention, and normative belief assessment. A full list of finalized survey questionnaires and messages will be submitted in a future modification to this study, before the online message testing commences.

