3. **Social media campaign (Phase 3):** The purpose of Phase 3 is to implement and evaluate an educational social media campaign for the public. Based on the results of Phase 1 and 2 studies to-date, we have identified a set of strong messages that improve parent attitudes and increase parents' intent to vaccinate their 9-14 year old child/ren for HPV. We will use these tested messages to launch a social media-based campaign via the Norris Cotton Cancer Center's Facebook page. We will deploy up to six campaign messages (see enclosed document with messages) to two groups of parents using Facebook's geo-targeting features, based on users' zip codes: 1) Parents in rural NH and VT and 2) Parents in urban NH and VT. We will measure each message's effectiveness by analyzing engagement data (provided by social media campaign metrics—all aggregate data with no individual identifiers), and attitudes and intent to vaccinate (to be assessed via online survey embedded in the social media campaign messages). See enclosed survey; parents with children of any age are invited to complete all questions except for questions related to their intention to vaccinate, which are limited to parents with 9-14 year old children. We will compare the differences between the two audience segments (rural vs. urban) and other subgroups that emerge from the data..

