#### 4. Analysis

**Describe any qualitative tests and measures as well as quantitative methods:**

1. **Online and local focus groups and message testing (Phases 1 & 2)-** Facebook comments, survey comments, and transcripts/audio files of the focus groups will be reviewed by the research team and coded for themes. We will also perform content and linguistic analyses. The self-reported survey measures will be examined for outliers and data skewness. Recording, transformation, or standardization will be made when necessary. We will conduct chi-square statistics for categorical variables and employ repeated GLM, ANOVA, ANCOVA, or regression statistics for continuous multivariate variables while controlling for relevant covariates. We will take structural equation modeling or path analyses to model persuasion pathways from message/ad exposure to changes in behavioral intentions to vaccinate. Based on persuasiveness scored rated for the HPV vaccine messages/ads, we will statistically test and select the

most highly-ranked messages/ads (best candidate messages/ads). These selected messages/ads will be used for the social media campaign.

2. **Social media campaign (Phase 3)-** We will measure message effectiveness by analyzing each message's effectiveness by assessing engagement data (provided by social media campaign metrics), and key constructs, including attitudes and intent to vaccinate (to be assessed via online survey embedded in the social media campaign messages). See enclosed survey; parents with children of any age are invited to complete all questions except for questions related to vaccination history and intention to vaccinate their 9-14 year old child/ren, which are limited to parents with 9-14 year old children. We will compare the differences between the two audience segments (rural vs. urban) or other subgroups of interest that emerge from the data. Although we do not solicit comments on Facebook, we expect that some Facebook users may leave comments/questions anyway; we will analyze the comments for themes and linguistic characteristics and compare between rural and urban audiences or by campaign themes (research team will de-identify all comments prior to analyses).

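### Phase 2 sets out to test change in intention and knowledge, but the protocol lists intention only after message exposure and knowledge only before it

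*Combined protocol and SAP*

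**What the plan says.** Objective 1 (Section 2) is to find messages and "measure their effectiveness to change parent attitudes and intentions to vaccinate their adolescent children".

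Section 3, item 2 (Online message testing, Phase 2) gives the aim as testing message effects "on changing knowledge, attitudes, beliefs, and behavioral intentions of parents of children 9-14 years old", and says: "The message testing phase will involve pre/post-test designs". It then lists what is measured when. The pre-test list is "prior knowledge, pre-existing attitudes, normative beliefs, response efficacy, and issue involvement". The post-test list is the persuasiveness of the message seen, followed by "attitude toward behavior promoted, response efficacy, behavioral intention, and normative belief assessment".

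Section 4, item 1 plans structural equation or path models to "model persuasion pathways from message/ad exposure to changes in behavioral intentions to vaccinate". It selects the campaign messages on their persuasiveness scores.

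Section 3, item 3 (Phase 3) reports that Phases 1 and 2 have identified messages that "improve parent attitudes and increase parents' intent to vaccinate". The Phase 3 items of Section 6 (risks) and Section 7 (unexpected events) repeat that the tested messages raised intention.

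**The concern.** A change score, or a post-test analysis adjusted for baseline, needs the same construct measured before and after exposure. On the lists given, intention has no pre-test value and knowledge has no post-test value, although change in both is a stated aim.

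Intention is the more serious half. It is one of the two outcomes in Objective 1 and the end point of the path model. Section 6 also uses the reported rise in its argument that risk to people who see the ads is low. Section 7 concedes that some messages could leave vaccine-hesitant parents less trusting, and intention measured only after exposure could not reveal a fall in intention. Without a baseline, high intention after a message cannot be told apart from high intention that was there already.

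**Working it through.** No figure in the plan needs reproducing for this point. The check is to set the two lists in Section 3, item 2 side by side and compare them with the stated targets.

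| Construct | Pre-test list | Post-test list | Where change is a target |
|---|---|---|---|
| Attitude | yes | yes | Phase 2 aim, Objective 1 |
| Normative belief | yes | yes | Phase 2 aim (beliefs) |
| Response efficacy | yes | yes | not named separately |
| Behavioral intention | no | yes | Phase 2 aim, Objective 1, path model |
| Knowledge | yes | no | Phase 2 aim only |
| Issue involvement | yes | no | none |
| Message persuasiveness | no | yes | none; used for selection |

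**Count.** The Phase 2 aim has four targets: two (attitudes, beliefs) are listed at both times and two (intention, knowledge) at one. Objective 1 has two outcomes: attitudes are listed at both times, intentions at one.

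**Does randomisation fill the gap?** Let Y0 and Y1 be a parent's intention before and after exposure, and let μ_m be the mean of Y1 under message m. Random assignment makes the expected value of Y0 the same, μ_0, under every message.

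- Difference between messages m and k: (μ_m − μ_0) − (μ_k − μ_0) = μ_m − μ_k. The baseline cancels, so post-test data alone can compare messages.
- Rise under message m: μ_m − μ_0. This contains μ_0, which needs either a pre-test item or a randomised group that sees no message.

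The Phase 2 data collection paragraph assigns participants to advertisement or message conditions, and no no-message condition is described. The same post-test means, in the same order, would therefore fit every message raising intention, none changing it, or some lowering it.

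**Does other text supply the missing items?** The Cohort 2B paragraph speaks of identical pre- and post-assessments, but it compares one cohort with another. It does not say that pre-test items match post-test items. Section 4 names no specific analysis of change in knowledge, so the knowledge gap touches the Phase 2 aim but no specified model.

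**The case against.** The strongest reply is that the lists are not the instrument. The pre-test constructs are called candidates, both lists are introduced with open wording, the final questionnaires are deferred to a later modification, and the data collection paragraph refers to an enclosed pre/post survey that is not in the text available. The lists are visibly incomplete: Section 13 says Phase 2 asks about risk perception, which is in neither list. The pre/post design, the repeated-measures models in Section 4 and the reported increases all suggest that intention may have been asked twice. An incomplete summary explains the text at least as well as a missing baseline does.

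This stands, and it limits the point. A reader might infer that change in intention cannot be computed, or that the reported increases have no baseline behind them. The documents do not support either inference, because they neither confirm nor rule out a pre-test intention item.

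Two further replies also stand. Selection rests on a post-exposure rating that needs no baseline, so the choice of campaign messages is not undermined. Randomisation allows a valid comparison of post-test intention between messages, and a path model from message condition to that outcome can be fitted.

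The replies do not remove the mismatch. The protocol calls its pre-test constructs critical to understanding message effectiveness, yet omits an Objective 1 outcome that it names at post-test. It also reports Phase 2 results while still giving only these lists.

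**Conclusion.** The point holds as a mismatch in the protocol text. Two of the four Phase 2 change targets, and one of the two Objective 1 outcomes, are listed at a single time point. If the lists were followed as written, the study could compare messages on post-exposure intention but could not show that intention rose.

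This rests on two readings: that the lists describe what was asked, which the enclosed survey could overturn, and that there is no no-message arm, since none is described. Knowledge is the lesser half, because it is outside Objective 1 and has no specified change analysis.

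No sample-size or power figure changes. The precision to be gained by adjusting for baseline depends on a pre/post correlation that the documents do not give, so no number is attached to it.

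**What to change.** Check the enclosed survey first.

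- **If intention was asked before and after exposure:** say so in Section 3, item 2.
- **If Phase 2 data are still to be collected:** add the same intention item or items to the pre-test list for parents of 9-14 year olds, and secondarily the same knowledge items to the post-test list.
- **Analysis in either case:** compare messages on post-test intention adjusted for its pre-test value, and report mean within-person change for each message. Without a no-message arm, that change remains a before-after difference, and the text should say so.
- **If the data were collected without pre-test intention:** limit the path-model outcome in Section 4 to post-exposure intention compared between messages, and remove the statements in Section 3 (item 3), Section 6 and Section 7 that intent increased. Do not replace them with a claim that the chosen messages gave higher intention than others, because the documents report no such result.
- **If knowledge was asked only before exposure:** take it out of the change aim.

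The cost is a few repeated items in a survey of about 15 minutes, or text edits alone. If the baseline cannot be recovered, the further cost is a weaker claim about intent.

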- a) *Sample size and recruitment:* We expect to test a finalized set of messages, up to approximately 40 messages, with up to 30 people evaluating each message; as such, we will recruit maximum 1,200 people to complete message testing via various media recruitment and platforms (including Amazon Mechanical Turk and social media advertisements). For message testing

[figure not shown]
experiments, we implement two different cohort studies (Cohort 2A and 2B in Figure 1). Additional people will be screened for eligibility.

**Cohort Phase 1B:** Previously IRB-approved Cohort 1B is no longer part of this study design. We did not have large enough sample size to conduct a time-lag follow-up study, thus this Cohort 1B is removed from the project.

**Cohort Phase 2A:** We use paid advertisements on social media and MTurk to recruit residents in VT and NH. An external link to Qualtrics surveys will be embedded in the ads and in the MTurk posting. The message testing study will be held on Qualtrics. We will measure same constructs and examine an identical set of candidate messages across two cohorts. This cohort will not have a time-lag between pre- and post-assessments.

**Cohort Phase 2B:** We will implement the same message testing study and recruit participants in the US via Mturk and social media advertisements (e.g., Facebook ads). MTurk is an online labor market with more than 500,000 active members where requesters distribute small tasks, and workers complete the tasks for compensation as low as 1 cent in US dollars. More than 345,000 tasks are available on MTurk to anonymous workers to complete. The cohort will be invited to the same message-testing experiments with identical pre- and post-assessments used in Cohort 1B and Cohort 2A. The data from this national pool of participants will be used as reference points. This cohort does not have a time-lag between pre- and post-assessments.

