## 9. Equitable Participant Selection

### a. Estimated number of participants at Dartmouth CPHS reviewed sites:

1. **Online focus groups and survey (Phase 1)-** We will seek up to 2,000 comments from parents (which could come from up to 2,000 parents) to identify salient themes for the top 40 candidate messages/materials for online message testing. We are seeking 200-300 pre-survey completions, with 200 people providing contact information for follow-up survey.

**2. Local focus groups and survey (Phase 1)**- We plan to conduct up to ten focus groups in all- up to five in rural communities and up to five in urban communities of New Hampshire and Vermont. We aim to have 8-12 participants in each group for ideal discussion facilitation. We will need to screen additional people for eligibility.

**3. Online message testing (Phase 2)**- We will enroll up to 1200 parents in the message testing (40 messages, 30 parents each). However, to achieve this, we expect that we may need to screen 2000+ parents.

**4. Social media campaign (Phase 3)**- The number of people who view the ads is difficult to estimate because of Facebook's algorithm in displaying ads to users. We would expect the ads to be displayed to tens of thousands of people throughout New Hampshire and Vermont, covering more than 75% of the target audience in the two states. For the evaluation survey, we will enroll everyone who is eligible and who consents to complete the survey, without setting an upper limit.

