**b. Provide a justification of the proposed sample size**

**1. Online focus groups (Phase 1)**- Given the possible number of messages to present to parents and the possible themes than may emerge in the comments, we feel up to 2,000 comments may be necessary to identify common themes in the comments.

**2. Local focus groups (Phase 1)**- In our experience, 8-12 people per group is reasonable to facilitate and meaningful for discussion. Given the different themes we are exploring, we expect that we may need as many as ten focus groups- five in rural areas and five in urban areas.

**3. Online message testing (Phase 2)**- We expect to evaluate a finalized set of up to 40 messages/materials. Based on our Co-PI's experience ([name]), we need at least 30 people to evaluate each message in order to determine its persuasiveness. Further, based on her experience, we also expect that about 40% of people screened will be eligible for the study, so we expect to screen at least 2000 people.

**4. Social media campaign (Phase 3)**- Our primary goal with the social media campaign is educating parents on this topic. As such, we are hoping to get as large of a reach as feasible across the Norris Cotton Cancer Center's catchment area of Vermont and New Hampshire. Because we are evaluating the effectiveness and acceptability of the campaign in a 'real world' setting across six messages and two sets of audiences, we are not setting an upper limit for the number of people who enroll and consent to complete the evaluation survey. Based on our experience with similar surveys, however, we do not expect more than 2,000 people to complete the survey.

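### Phase 2 treats 30 raters per message as both a minimum and a maximum, with no margin at 40 messages, and the 2,000 to be screened does not follow from 40% eligible

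*Combined protocol and SAP*

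**What the plan says.** In Phase 2 each participant is randomised to one message condition (Section 3, item 2), so the number of participants equals the number of message ratings. The relevant statements are:

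- Section 3, item 2, a): "up to approximately 40 messages, with up to 30 people evaluating each message; as such, we will recruit maximum 1,200 people". This is the only place that sets an upper limit per message.
- Section 9.b, item 3: "we need at least 30 people to evaluate each message in order to determine its persuasiveness".
- Section 9.a, item 3: "We will enroll up to 1200 parents in the message testing (40 messages, 30 parents each". This caps the total and shows how it is made up.
- Screening, Section 9.b, item 3: "about 40% of people screened will be eligible for the study, so we expect to screen at least 2000 people". Section 9.a, item 3 has "we expect that we may need to screen 2000+ parents".
- Cohorts 2A (New Hampshire and Vermont) and 2B (United States), Section 3, item 2, a): "We will measure same constructs and examine an identical set of candidate messages across two cohorts". Of Cohort 2B: "The data from this national pool of participants will be used as reference points".
- Who may take part, Section 3, item 2: "parents of any age child are invited to complete the survey as well, excluding questions related to vaccination history and intention to vaccinate".

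No allowance is stated for unusable surveys or for uneven numbers per message, and the method of random assignment is not described.

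**The concern.** Thirty raters per message is the only basis given for the size of Phase 2. There is no effect size, standard deviation, error rate or power. Section 9.b presents 30 as what is needed to judge a message's persuasiveness, and Section 4 then selects campaign messages from the persuasiveness scores. If 30 is a requirement, the design section should not make it a limit, and the total should leave room for ordinary losses.

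The screening number raises a separate problem. Section 9.b offers it as a consequence of the eligibility rate, and it is not one. Anyone planning recruitment from that sentence would expect a yield one third below the enrolment figure.

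**Working it through.** **Inputs.** Up to 40 messages, 30 raters each and a total of 1,200 (Sections 3, 9.a and 9.b); 40% eligible and 2,000 screened (Section 9.b). Loss rates and the assignment method are not given, so they are assumed where marked.

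**1. Reproduce the enrolment figure.** 40 × 30 = 1,200. It reproduces exactly. Both cohorts rate the same messages under this one total, so the 30 is reached at 40 messages only if the cohorts are pooled.

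**2. Margin by number of messages (1,200/m).** 40 messages: 30 each. 36: 33.3. 30: 40. 20: 60. The margin is zero only at the full 40. With fewer messages there is slack in the total, but the per-message ceiling in Section 3 still conflicts with the floor in Section 9.b.

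**3. Effect of unusable surveys at 40 messages (assumed range).** Usable raters per message = 30 × (1 − d); enrolment needed to keep 30 = 1,200/(1 − d), rounded up.

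- d = 5%: 28.5 per message; 1,264 needed.
- d = 10%: 27; 1,334.
- d = 20%: 24; 1,500.

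**4. Effect of uneven assignment (assumed simple, unrestricted randomisation).** With 1,200 people over 40 messages, 50,000 simulated allocations left about 19 messages below 30 on average, with a median smallest group of 19. Balanced assignment would remove this.

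**5. Attempt to reproduce the screening figure.**

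- Yield: 2,000 × 0.40 = 800, against 1,200. The shortfall is 400, or 400/1,200 = 33%.
- Per message: 800/40 = 20. At 30 each, 800/30 = 26.7, enough for 26 messages.
- Screening needed: 1,200/0.40 = 3,000.
- Eligible share implied by 2,000: 1,200/2,000 = 60%. Since 1,200/(1 − 0.40) = 2,000 exactly, the 40% may have been meant as the ineligible share.

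**6. Could parents of other-age children close the gap?** If the 40% counts only parents of 9-14 year olds, a further 400 of the 2,000 screened (20%) would have to be other parents. They skip the intention items, so intention would rest on 800 people, 20 per message at 40 messages. The plan sets no per-message target for intention.

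**7. What 30 versus 20 means (illustration).** The unadjusted 95% half-width for a difference between two message means is t × √(2/n). At n = 30: 2.00 × 0.258 = 0.52 SD. At n = 20: 2.02 × 0.316 = 0.64 SD. Adjustment for pre-test scores would narrow both. The plan does not specify this pairwise contrast.

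**The case against.** The plan has several defences. Forty messages is an upper limit. The 1,200 in Section 3 can be read as people who complete testing, in which case dropouts are already outside the count. Section 5 provides for checking data during collection, following up missing blocks, further recruitment and a survey quota. Both screening figures are lower bounds, and Section 3 expects additional people to be screened. Finally, Section 3, item 3 and Sections 6.a and 7 show that campaign messages have already been tested and chosen.

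Much of this stands, and it limits the point. It does not reconcile a ceiling of 30 with a floor of 30. The quota in Section 5 is for the survey as a whole, so it does not protect individual messages. A lower bound of 2,000 is not breached by screening 3,000, but it is still presented as following from 40%.

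Four stronger readings are tempting and are not supported:

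- That Phase 2 would enrol, or did enrol, only 800. Nothing caps screening.
- That the selected messages had fewer than 30 raters. No achieved numbers are given, and the assignment method is unstated, so neither balance nor imbalance is documented.
- That Section 9.a also limits raters per message. It limits only the total.
- That 30 is meant for each cohort, which would need 2,400 at 40 messages. The product 40 × 30 = 1,200 points to pooling, although the text does not say so.

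**Conclusion.** The point holds as an internal inconsistency in wording and arithmetic. The required 30 per message equals the maximum possible average at 40 messages, so at that size the minimum is met for every message only if the cohorts are pooled, assignment is even and all 1,200 ratings are usable. With fewer messages only the wording conflict remains.

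The screening number and the eligibility rate cannot both be right for 1,200 enrolled, unless parents of other-age children are additional to the 40%. The gap is 800 against 1,200 enrolled, or 2,000 against 3,000 screened. The documents do not show which input is wrong, so 3,000 should not be taken as the correction by default.

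The arithmetic uses only the plan's figures. The results for unusable surveys and simple randomisation rest on the stated assumptions. With message selection already made, the practical weight falls on reporting how many people actually rated each message.

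**What to change.** 1. In Section 3, item 2, a), replace the per-message ceiling with wording that agrees with Section 9.b, and say that the 30 are completed ratings pooled over Cohorts 2A and 2B. Then do one of two things: limit the number of messages so that 1,200 gives more than 30 each (1,200 × 0.90/30 = 36 messages if 10% of surveys are assumed unusable), or describe 30 as the expected average at 40 messages. Calling 30 a minimum while keeping both 40 messages and 1,200 people would leave the margin at zero.
2. In Sections 9.a and 9.b, correct whichever screening input is wrong: at least 3,000 screened if 40% is the eligible share, or 60% eligible if 2,000 is right. State whether parents of other-age children are counted in that share.
3. For any testing that remains, use evenly balanced random assignment within cohort, counting completed post-tests.
4. For testing already done, report the achieved number per message by cohort, and separately for the intention items.

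The cost is wording in three places, one table and, if testing continues, a change to how the survey allocates messages. The downside is a less favourable stated figure. The cost of further screening cannot be bounded: the plan gives the MTurk screener payment but not the spend on paid advertisements.
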